- In clinical studies done in the CCR, M7824 as monotherapy has produced a notable objective response rate (35-40%) for metastatic HPV + cancers including Oropharyngeal Squamous Cell Carcinoma (OPSCC) and preclinical studies support the addition of an investigational HPV vaccine with therapeutic intent (PRGN-2009, a gorilla adenoviral based vaccine) to further increase anti-tumor efficacy.

Objectives:

Phase I in participants with recurrent/metastatic HPV positive cancer:

- Primary objective: To determine the safety and recommended phase II dose (RP2D) of PRGN-2009 (HPV vaccine) alone or in combination with M7824 administered at RP2D of 1200 mg q2w.

Phase II in participants with newly diagnosed stage I (T1,T2 N1)/II/III p16-positive oropharyngeal cancer and patients with newly diagnosed operable stage II/III/IVA/IVB HPV+ sinonasal squamous cell cancer:

- Primary objective: To determine if HPV vaccine alone (Arm 2A) is able to result in a ≥ 2 -fold increase in CD3+ tumor infiltrating T cells post treatment compared with pre-treatment in p16-positive oropharyngeal cancer.

Eligibility:

Phase I:

- Men or women of age ≥ 18 years old.

Abbreviated Title: Combo Immunotx in HPV OPSCC

Version Date: 09.20.2023

- Subjects with cytologically or histologically confirmed locally advanced not amenable to potentially curative local therapies or metastatic HPV associated malignancies:
 - Cervical cancers;
 - p16+ Oropharyngeal cancers;
 - Anal cancers;
 - Vulvar, vaginal, penile, and squamous cell rectal cancers
 - Other locally advanced or metastatic solid tumors (e.g., lung, esophagus) that are known HPV+.
- Prior first line systemic therapy is required.

Phase II:

- Men or women of age \geq 18 years old.
- Subjects with newly diagnosed stage I (T1,T2 N1), II or III p16-positive oropharyngeal squamous cell carcinoma (OPSCC) or stage II/III/IVA/IVB HPV-SNSCC planned for definitive therapy.

Design:

Phase I: Recurrent/metastatic HPV associated cancer:

- A 3+3 dose escalation design will be used which will evaluate PRGN-2009 (HPV vaccine) at two dose levels (1×10^{11} and 5×10^{11} viral particle (VP) units) given as monotherapy followed by a third dose level evaluating the RP2D dose of PRGN-2009 in combination with 1200 mg (RP2D) of M7824. In addition, the combination of PRGN-2009 at RP2D with 1200 mg of M7824 will be expanded to a total of 10 evaluable participants to gauge the preliminary efficacy of the combination of PRGN-2009 and M7824 in participants with advanced disease.
- There will be a 4-week DLT evaluation period for each dose level.
- It is expected that up to 22 participants may enroll.

Phase II:

- Newly diagnosed p16-positive oropharyngeal cancer:
 - Evaluation of HPV vaccine alone (Arm 2A: Stage I (T1,T2 N1)/II/III) as neoadjuvant/ induction therapy before definitive standard of care therapy.
 - Participants will receive neoadjuvant/ induction immunotherapy at NIH Clinical Center and then be referred back to their home institution for definitive standard of care therapy.
 - It is expected that up to 20 participants may enroll.
- Newly diagnosed stage II/III/IVA/IVB HPV-SNSCC:
 - Enrollment and treatment will occur similarly as participants with p16+ oropharyngeal cancer for exploratory correlates to advise possible future trials. Up to 2 participants may enroll in this group.

TABLE OF CONTENTS

PRÉCIS.....	2
TABLE OF CONTENTS	4
STATEMENT OF COMPLIANCE	7
1 INTRODUCTION	8
1.1 Study Objectives	8
1.2 Background and Rationale.....	9
2 ELIGIBILITY ASSESSMENT AND ENROLLMENT	20
2.1 Eligibility Criteria	20
2.2 Screening Evaluation	23
2.3 Participant Registration and Status Update Procedures.....	24
2.4 Baseline Evaluation.....	25
3 STUDY IMPLEMENTATION	27
3.1 Study Design.....	27
3.2 Drug Administration	29
3.3 Dose Modifications.....	30
3.4 Study Calendar.....	39
3.5 Cost and Compensation	45
3.6 Criteria for Removal from Protocol Therapy and Off Study Criteria.....	45
4 CONCOMITANT MEDICATIONS/MEASURES	46
4.1 Permitted Medications	46
4.2 Prohibited Medications	46
5 CORRELATIVE STUDIES FOR RESEARCH	48
5.1 Biospecimen Collection	48
5.2 Sample Storage, Tracking and Disposition.....	52
6 DATA COLLECTION AND EVALUATION	55
6.1 Data Collection	55
6.2 Data Sharing Plans.....	56
6.3 Response Criteria	56
6.4 Toxicity Criteria.....	63
7 NIH REPORTING REQUIREMENTS / DATA AND SAFETY MONITORING PLAN...63	63
7.1 Definitions.....	63

7.2	OHSRP Office of Compliance and Training / IRB Reporting.....	63

The protocol, informed consent form(s), recruitment materials, and all participant materials will be submitted to the Institutional Review Board (IRB) for review and approval. Approval of both the protocol and the consent form must be obtained before any participant is enrolled. Any amendment to the protocol will require review and approval by the IRB before the changes are implemented to the study. In addition, all changes to the consent form will be IRB-approved; an IRB determination will be made regarding whether a new consent needs to be obtained from participants who provided consent, using a previously approved consent form.

1 INTRODUCTION

1.1 STUDY OBJECTIVES

1.1.1 Primary Objectives

Phase I in participants with recurrent/metastatic HPV positive cancer:

- Primary objective: To determine the safety and recommended phase II dose (RP2D) of PRGN-2009 (HPV vaccine) alone or in combination with M7824 administered at RP2D of 1200 mg q2w.

Phase II in participants with newly diagnosed stage I (T1,2 N1)/II/III p16-positive oropharyngeal cancer (OPSCC) cancer:

- Primary objective: To determine if HPV vaccine alone (Arm 2A) is able to result in a ≥ 2 -fold increase in CD3+ tumor infiltrating T cells post treatment compared with pre-treatment in p16-positive oropharyngeal cancer.

1.1.2 Secondary Objectives

Phase I in participants with recurrent/metastatic HPV positive cancer:

- To assess overall response rate (ORR) according to RECIST 1.1.
- To assess progression-free survival time (PFS).
- To assess overall survival (OS).
- To assess duration of response.
- To assess ratio of participants that are hospitalized because of adverse events attributed to disease progression.

Phase II in participants with newly diagnosed stage I (T1,2 N1)/II/III p16-positive oropharyngeal cancer (OPSCC) cancer:

- To determine if the use of PRGN-2009 alone results in significantly prolonged survival as compared to the expected 80% three-year historical survival for this population.
- To determine the 3-year overall and relapse-free survival rate for PRGN-2009 alone (Arm 2A) as neoadjuvant/ induction therapy before definitive standard of care therapy for this population.
- To assess the safety of the recommended phase II dose (RP2D) of PRGN-2009 (HPV vaccine) alone in this participant population.

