Human papilloma virus (HPV)-positive oropharyngeal squamous cell carcinoma (OPSCC) now represents the most common HPV-associated malignancy in the United States and the incidence is rising (13, 14). Over 80% of OPSCC is HPV-positive, and nearly all HPV-positive OPSCC are caused by HPV 16 or 18. Definitive standard-of-care treatment for patients with stage II/III HPV-positive oropharyngeal head and neck squamous cell carcinoma most commonly includes multi-

modality treatment consisting of concurrent chemotherapy and radiation (CRT) (15). Surgery is rarely utilized due to the morbidity associated with resection of oropharyngeal tissues. Despite maximum treatment, 20% of patients with stage II and 35% of patients with stage III disease will die within 4 years of diagnosis (Figure 1)(16). In patients cured of their disease, treatment often results in dysfunctional swallowing, taste, and speech as well as in extensive tissue fibrosis and pain (17). Patients with HPV-positive OPSCC are diagnosed at a younger age, making the long-term morbidity associated with concurrent CRT particularly concerning. Induction treatment strategies that have the goals of both decreasing disease recurrence and increasing survival permit the future study of definitive treatment de-intensification (18). Attempts to de-intensify treatment of HPV-positive OPSCC by replacing cisplatin chemotherapy with the EGFR monoclonal antibody (mAb) cetuximab have failed (15). Stage I (AJCC 8th edition) includes patients with T0-2 and N0-1 disease. Treatment within Stage I is not uniform. Recommended treatment for T1-2 N0 disease is definitive radiotherapy or surgical resection with or without ipsilateral/bilateral neck lymph node dissection and risk-stratified adjuvant treatment. Recommended treatment for T1-2 N1 with 1 lymph node (ipsilateral) not larger than 3 cm is definitive chemoradiotherapy or radiotherapy or surgical resection with or without ipsilateral/bilateral neck lymph node dissection and risk-stratified adjuvant treatment. Recommended treatment for T1-2 N1 with 1 lymph node (ipsilateral) larger than 3 cm or 2 or more ipsilateral lymph nodes none larger than 6 cm follows the paradigm of Stage II disease, with definitive chemoradiotherapy or resection plus adjuvant treatment. Consequently, while the prognosis for Stage I patients is better than Stage II and III, there is a need for de-intensification of treatment in Stage I T1-2 N1 disease.

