10.1.2 Secondary Endpoints

10.1.2.1 Phase I:

The secondary endpoint of the phase I portion of the study are to determine overall response rate (ORR), progression-free survival time (PFS), overall survival (OS), ratio of participants that are hospitalized because of adverse events attributed to disease progression, and duration of response of the combination therapy in participants with advanced disease.

10.1.2.2 Phase II:

The secondary endpoints of the phase II portion of the study are:

- To determine if the use of HPV vaccine alone results in potentially prolonged survival as compared to the expected 80% three-year historical survival for this population.
- To determine the 3-year overall and relapse-free survival rate for HPV vaccine alone (Arm 2A) in combination with standard of care chemoradiation in participants with p16+ oropharyngeal cancer.

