10.2 SAMPLE SIZE DETERMINATION

The phase I portion of the trial will be conducted using 3+3 dose escalation design evaluating the safety of PRGN-2009 at two dose levels as monotherapy and at the RP2D of PRGN-2009 in combination with a fixed dose of M7824. Using this design up to 22 participants may be enrolled on the phase I portion of the study.

In arm 2A, phase II, 20 participants with p16+ oropharyngeal cancer will be enrolled based on the following reasoning. Assume that a success for any individual participant will be defined as that participant experiencing a two-fold increase in CD3+ tumor infiltrating T cells post treatment compared with pre-treatment. With 20 participants, there would be 80.4% power to detect a difference between 50% and 80% of participants experiencing a success in arm 2A, with an exact binomial test using a one-sided 0.05 significance level. As an illustration, with 20 participants, if 15 participants were able to have a two-fold increase, the lower two-sided 90% confidence bound on 15/20 is 54.4% and the upper two-sided 90% confidence bound is 89.6%. Thus, 15/20 participants would demonstrate the intended magnitude of effect. If 14/20 had this outcome, the lower 90% two-sided bound is 49.2% and the upper two-sided 90% bound is 86.0%, essentially demonstrating nearly the same result.

Expecting that up to 22 evaluable participants will enroll on the phase I portion of the study, that 20 evaluable p16+ oropharyngeal cancer participants will enroll on phase II 2A, and that up to 2 evaluable HPV-SNSCC participants may enroll on phase II 2A, a total of up to 44 evaluable participants will be planned to enroll on this protocol. To allow for a few inevaluable participants the accrual ceiling for this protocol will be set at 50 participants.

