10.4.3 Analysis of the Secondary Endpoints

For the phase I portion of the study data will be obtained on ORR, duration of response, PFS, OS, and ratio of participants that are hospitalized because of adverse events attributed to disease progression.

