10.4.4.3 Overall Survival

OS will be evaluated using Kaplan-Meier methods. OS will be defined as the time from the date of first treatment to the date of death (any cause). Subjects who are alive at the end of follow up will be censored at the last known date alive.

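### Section 1.1.2 promises a significance conclusion on survival against a fixed 80% three-year rate, but Section 10 plans no such test and the 80% carries no source or stage mix where it is used

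*Combined protocol and SAP*

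**What the plan says.** Section 1.1.2 sets a phase II secondary objective of "significantly prolonged survival as compared to the expected 80% three-year historical survival for this population". Section 10.1.2.2 states the same endpoint as "potentially prolonged survival as compared to the expected 80% three-year historical survival for this population". Neither place cites a source for the 80% or says which stages it describes.

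On analysis, Section 10.4.3 reads "For the phase I portion of the study data will be obtained on ORR, duration of response, PFS, OS" and does not mention phase II. The subsections after it do reach phase II: 10.4.4.1 defines relapse-free survival from the end of chemoradiation, and 10.4.4.3 says "OS will be evaluated using Kaplan-Meier methods". None of them gives a null value, test, alpha, confidence interval or success rule for the comparison with 80%.

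The only sizing is in Section 10.2, for doubling of the CD3+ infiltrate: "80.4% power to detect a difference between 50% and 80% of participants experiencing a success in arm 2A".

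On prognosis by stage, Section 1.2.1 says "20% of patients with stage II and 35% of patients with stage III disease will die within 4 years of diagnosis". Of stage I it says "while the prognosis for Stage I patients is better than Stage II and III", without a number. It adds that part of T1-2 N1 disease "follows the paradigm of Stage II disease" in its treatment. Arm 2A accepts stage I (T1,2 N1), II and III, with no cap or stratification by stage.

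Two related places matter. Section 10.1.3 repeats the 80% bullet as an exploratory endpoint without naming a disease. Section 10.3 limits the survival set to participants who had two doses and went on to definitive therapy, while 10.4.4.3 starts OS at first treatment.

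**The concern.** The word *significantly* commits the trial to an inferential conclusion. A reader of Section 1.1.2 would expect a hypothesis, a test and an error rate, and Section 10 has none. If a test is chosen once the data are visible, the answer may depend on the choice.

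The comparator adds a second difficulty. A fixed 80% is interpretable only if the enrolled patients resemble those behind it. With three stages of different prognosis, an unknown stage mix behind the 80% and an uncontrolled mix in the arm, a result above or below 80% cannot be assigned to the vaccine rather than to who was enrolled.

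What is at stake is the interpretation of one secondary objective: an unsupported claim of survival benefit, or of its absence.

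**Working it through.** **1. The plan's own sizing (Section 10.2).** Exact binomial, n = 20, null 50%, alternative 80%, one-sided 0.05. The critical value is 15: P(X ≥ 15 | 0.50) = 0.0207 and P(X ≥ 15 | 0.80) = 0.804. The stated 80.4% reproduces, as do the 90% limits (54.4% to 89.6% for 15/20; 49.2% to 86.0% for 14/20). This calculation concerns CD3+ doubling. The 80% in it is the alternative success rate and has nothing to do with survival.

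**2. The same test applied to survival.** The plan names no survival test, so this is an illustration. It uses n = 20, null 80% at three years, one-sided 0.05, and assumes three-year status is known for all.
- P(20/20 | 0.80) = 0.80^20 = 0.0115, which rejects.
- P(X ≥ 19 | 0.80) = 20 × 0.80^19 × 0.20 + 0.80^20 = 0.0692, which does not.
- Power therefore equals the chance of 20/20: 0.90^20 = 0.122 at a true 90%, and 0.95^20 = 0.358 at a true 95%. The 90% and 95% are assumed alternatives.

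**3. Sensitivity to the test chosen.** One-sample log-rank, Z = (O − E)/√E, rejecting below −1.645. Here O is observed deaths and E is the null hazard −ln(0.80)/3 = 0.0744 per year times follow-up. Constant hazard and no dropout are assumed, and the test was simulated.

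| Test | True 90% | True 95% |
|---|---|---|
| Exact binomial at 3 years | 12% | 36% |
| Log-rank, 3 years | 12% | 36% |
| Log-rank, all followed 5 years | 35% | 78% |

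**4. Precision.** Clopper-Pearson 95% intervals: 17/20 alive gives 62% to 97%; 19/20 gives 75.1% to 99.9%, still including 80%; 20/20 gives 83.2% to 100%.

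**5. What stage mix the 80% could represent.** Section 1.2.1 gives four-year survival of 80% (stage II) and 65% (stage III). At constant hazard (an assumption), three-year survival is 0.80^(3/4) = 0.846 and 0.65^(3/4) = 0.724.
- With no stage I, the stage II share giving 80% is (0.800 − 0.724)/(0.846 − 0.724) = 0.62.
- With stage I at an assumed 90% and the rest split II:III between 50:50 and 30:70, the stage I share giving 80% is 0.13 to 0.28.

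Several mixes fit, so the figure does not reveal its own.

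**6. Direction of the stage effect with no vaccine effect.** Stage I survival is assumed at 85% to 95%.
- Half stage I, the rest at 80%: 0.5 × S_I + 0.5 × 0.80 = 82.5% to 87.5%.
- Half stage I, the rest II:III at 25:75 (0.25 × 0.846 + 0.75 × 0.724 = 0.754): 80.2% to 85.2%.
- 20% I, 20% II, 60% III: 0.2 × S_I + 0.2 × 0.846 + 0.6 × 0.724 = 77.4% to 79.4%.

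The shift can go either way, and its size depends on rates and shares that the text does not give.

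**7. The bullet in 10.1.3.** Because no disease is named, it either duplicates 10.1.2.2 or applies to sinonasal participants. There are at most 2 of these, and Section 1.2.2 gives only a five-year OS for them (68.1% to 80.0%).

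**The case against.** The strongest reply is that this is one adverb. Section 10 already says *potentially*, the next bullet in both places already asks for the three-year OS and relapse-free rates, and Kaplan-Meier estimation is planned. A secondary objective need not be powered, so sizing on CD3+ alone is normal. All of this stands. It narrows the point to a claim in 1.1.2 that the analysis plan does not back, plus a missing interval. It does not remove the point, because both wordings are current text and promise different conclusions.

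Three stronger readings are tempting, and the documents do not support them.
- **The trial is underpowered for survival, and that is an error.** No survival test or power is claimed. The figures above show only that the word *significantly* has nothing behind it.
- **Enrolling stage I inflates survival against 80% by a known amount.** No stage I rate is in the text, the shift can be downward, and under the binomial test no-effect rejection with half the arm stage I is only 0.825^20 = 2% to 0.875^20 = 7%. Sampling error in 20 patients is far larger than these shifts.
- **The 80% is wrong or has no basis.** Section 1.2.1 cites a stage-specific source, and Figure 1 shows stage-specific survival but is not reproduced in the text available. It may support 80%. What can be said is that no link is made where the figure is used.

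A further fair objection is that replacing a pre-set benchmark with one computed after enrolment in an open-label arm creates its own risk. That is accepted in the remedy.

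**Conclusion.** The concern holds in a limited form. Section 1.1.2 promises a significance conclusion, disagrees with 10.1.2.2, and has no test behind it. Under the primary endpoint's own test, only 20/20 alive would reject 80%, with 12% power at a true 90% and 36% at a true 95%. A more favourable five-year log-rank test would give 35% and 78%, so the answer would depend on a choice that the plan does not make. This part is firm and rests on the text and exact arithmetic; the log-rank figures also need constant hazard and complete follow-up.

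The stage-mix part is firm in principle only. The 80% is not tied to a source or mix, and stages of different prognosis enter without a cap, so a difference from 80% in either direction could partly reflect case mix. Its magnitude cannot be fixed from the documents.

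The survival set is a further, unquantified bias. Anyone who dies or drops out before definitive therapy is excluded although the clock starts at first treatment, which favours the arm against a historical rate. Table 8 lists no grade 5 events among 22 phase 2 participants, so the effect of early deaths may be small, but other exclusions are unknown.

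The primary endpoint, sample size and halting rules are not affected.

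**What to change.** 1. Reword Section 1.1.2 to a descriptive Kaplan-Meier three-year OS with a 95% confidence interval and no significance claim, and align 10.1.2.2 with it.
2. Keep the 80% as the pre-set reference, stating its source and stage mix. Beside it, report an expected three-year OS weighted by the enrolled stage mix. Take the stage rates from the stage-specific source already cited in Section 1.2.1, and write them into Section 10 before three-year OS is analysed.
3. Remove the 80% bullet from 10.1.3, or name the disease it concerns.
4. Report OS from first treatment for all treated oropharyngeal participants alongside the evaluable set of Section 10.3.

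The cost is protocol wording and one weighted average, with no change to accrual. Table 8's 22 phase 2 participants match the planned 20 plus 2, so the enrolled mix is probably already known, although the table gives no stages. For item 4, Section 3.3.1 keeps participants who stop for toxicity under survival follow-up. The long-term follow-up footnote in 3.4.2 speaks of those who completed induction, so one sentence there may be needed.

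The downside is that published stage I data also cover T0 and N0 disease and may not match T1-2 N1. The comparison also remains non-randomised and descriptive whatever benchmark is used.

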1.1.3 Exploratory Objectives

Phase I and Phase II

- To conduct exploratory immunologic studies to understand and improve the administered treatment, including:
 - To examine the pharmacokinetics of bintrafusp alfa while on treatment.
 - To determine the ORR per RECIST v1.1 of combination of PRGN-2009 and M7824 in participants with advanced HPV associated malignancies

- Precigen, Inc. may analyze samples to be used for additional exploratory analyses, to further investigate:
 - HPV 16/18 -specific immune responses, activation status of the immune system, anti-tumor specific immune responses induced by the exposure to PRGN-2009.

Phase II only

- To determine the rate of objective response following neoadjuvant/induction immunotherapy alone per RECIST 1.1.
- To assess changes in salivary HPV DNA from pre-treatment and compared to during neoadjuvant/induction therapy with PRGN-2009 (HPV vaccine) alone in participants with HPV-OPC.
- To determine the feasibility and safety of neoadjuvant treatment therapy with PRGN-2009 (HPV vaccine) alone in participants with HPV-SNSCC.
- To assess the differences in CD3+ tumor infiltrating lymphocytes following neoadjuvant therapy with PRGN-2009 (HPV vaccine) alone in participants with HPV-SNSCC.
- To determine the objective response rate following neoadjuvant therapy with PRGN-2009 (HPV vaccine) alone in participants with HPV-SNSCC.

1.2 BACKGROUND AND RATIONALE

1.2.1 HPV Associated Malignancies

In the United States, there are more than 30,000 cases of HPV associated cancer annually (1) (Table 1). Metastatic HPV associated malignancies (cervical, anal, oropharyngeal cancers etc.) are often incurable and poorly palliated by standard therapies. Responses to chemotherapy are variable but generally short-lived with median PFS around 3 to 7 months (2-5). In a Gynecologic Oncology Group randomized trial comparing four cisplatin-based doublets as first line therapy for metastatic cervical cancer the response rates were 22-29% and median PFS was 4 to 6 months with median OS 10 to 13 months (6). The addition of bevacizumab to combination chemotherapy has been reported to increase OS by 3.7 months, but virtually all patients die of their disease within 2 years (7). Randomized trials of second line therapy are lacking but response rates for single agents are generally reported to be less than 20% (8). Early evidence suggests that immune checkpoint therapy also has a low response rate in this disease with a phase 1b trial (KEYNOTE 028) showing a 12.5% response rate (3/24 patients) and a phase II study showing a response rate of 13.3% (13/98 patients) to pembrolizumab in patients with recurrent or metastatic cervical cancer (9).

Table 1: Estimated annual incidence of HPV associated cancers in the US

Site	Incidence of HPV associated cancers	Cases attributed to HPV (%)
Oropharyngeal	15,738	11,000 (70.1%)
Cervix	11,771	10,700 (90.6%)
Vulvar	3554	2400 (68.8%)

Site	Incidence of HPV associated cancers	Cases attributed to HPV (%)
Vaginal	802	600 (75%)
Penis	1168	700 (63.3%)
Rectal (squamous cell)	750	700 (91.1%)
Anus	5,010	4,600 (91.1%)
Total	38,793	30,700 (79.1%)

For metastatic oropharyngeal cancer, the best estimates of the chemotherapy responsiveness are inferred from looking at the oropharyngeal site in subset analyses from clinical trials for head and neck cancers. In a pivotal clinical trial that established platinum, 5-fluorouracil (5-FU), plus cetuximab as first line therapy in head and neck cancer, patients with oropharyngeal tumors experienced PFS of 4 to 6 months and OS of 8 to 11 months (3). Immune checkpoint therapy has become the standard second line therapy for metastatic oropharyngeal cancer but response rates are still low with this therapy. As an example, the phase 1b trial (KEYNOTE-012) of pembrolizumab which led to its FDA approval for recurrent or metastatic head and neck squamous cell carcinoma (HNSCC) as second line therapy had a 17.7% response rate (34/192 patients). Response rates were slightly better in HPV positive HNSCC (21.9%) (10), but still occurred in only a minority of the patients. More recently pembrolizumab had been FDA approved as first line therapy for metastatic PD-L1 expressing HNSCC but the response rate for pembrolizumab alone in this setting is still only 16.9%.

In regard to metastatic anal cancer, only a handful of randomized trials have been performed in the last 30 years. In the metastatic setting, most of the evidence is limited to small phase II trials, retrospective series, and case reports. A recent retrospective series looking at 77 patients, 44 (55%) of whom received 5-FU in combination with cisplatin, 24 (31%) of whom received carboplatin + paclitaxel, and 11 (14%) of whom received another regimen showed a median PFS of 7 months and median OS of 22 months (5). As with HNSCC, recent early phase trials evaluating immune checkpoint therapy in this disease have shown that responses here too are limited to around 20% of patients treated. A recent phase II trial of nivolumab for metastatic squamous cell anal cancer showed a 21% response rate (7/33 patients) and a recent phase IB trial (KEYNOTE-028) of pembrolizumab showed a 20% response rate (5/25 patients) (11). In a recently published phase II trial, Massarelli et al. evaluated the combination of a therapeutic HPV vaccine and Nivolumab (12). In contrast to previous single therapy immune checkpoint inhibitor trials, they found an overall response rate of 33% showing the potential benefit of Immuno-Oncology (I/O) combination therapy for these diseases.

[figure not shown]
Human papilloma virus (HPV)-positive oropharyngeal squamous cell carcinoma (OPSCC) now represents the most common HPV-associated malignancy in the United States and the incidence is rising (13, 14). Over 80% of OPSCC is HPV-positive, and nearly all HPV-positive OPSCC are caused by HPV 16 or 18. Definitive standard-of-care treatment for patients with stage II/III HPV-positive oropharyngeal head and neck squamous cell carcinoma most commonly includes multi-

modality treatment consisting of concurrent chemotherapy and radiation (CRT) (15). Surgery is rarely utilized due to the morbidity associated with resection of oropharyngeal tissues. Despite maximum treatment, 20% of patients with stage II and 35% of patients with stage III disease will die within 4 years of diagnosis (Figure 1)(16). In patients cured of their disease, treatment often results in dysfunctional swallowing, taste, and speech as well as in extensive tissue fibrosis and pain (17). Patients with HPV-positive OPSCC are diagnosed at a younger age, making the long-term morbidity associated with concurrent CRT particularly concerning. Induction treatment strategies that have the goals of both decreasing disease recurrence and increasing survival permit the future study of definitive treatment de-intensification (18). Attempts to de-intensify treatment of HPV-positive OPSCC by replacing cisplatin chemotherapy with the EGFR monoclonal antibody (mAb) cetuximab have failed (15). Stage I (AJCC 8th edition) includes patients with T0-2 and N0-1 disease. Treatment within Stage I is not uniform. Recommended treatment for T1-2 N0 disease is definitive radiotherapy or surgical resection with or without ipsilateral/bilateral neck lymph node dissection and risk-stratified adjuvant treatment. Recommended treatment for T1-2 N1 with 1 lymph node (ipsilateral) not larger than 3 cm is definitive chemoradiotherapy or radiotherapy or surgical resection with or without ipsilateral/bilateral neck lymph node dissection and risk-stratified adjuvant treatment. Recommended treatment for T1-2 N1 with 1 lymph node (ipsilateral) larger than 3 cm or 2 or more ipsilateral lymph nodes none larger than 6 cm follows the paradigm of Stage II disease, with definitive chemoradiotherapy or resection plus adjuvant treatment. Consequently, while the prognosis for Stage I patients is better than Stage II and III, there is a need for de-intensification of treatment in Stage I T1-2 N1 disease.

In this clinical trial, we are studying immunotherapy consisting of PRGN-2009, an investigational HPV vaccine with therapeutic intent with or without M7824, a dual PD-L1 and TGF beta inhibitor, first as a phase I study to assess safety and tolerability, then as a phase II induction “window of opportunity” study with treatment before and after definitive therapy for patients with newly diagnosed stage I (T1,2 N1)/II/III HPV-positive OPSCC.

